#### (2) Research Procedures and Participant Cooperation:

Collect basic participant information (body mass index, body fat, etc.), followed by muscle function tests (muscle strength parameters, posture assessment) conducted by a physical therapist. The treatment plan includes 12 weeks of post-surgical or post-intervention orofacial myofunctional training, with pre- and post-surgical measurements and follow-up tests (Figure 2). Measurement items include drug-induced sleep endoscope examination and CT scans performed by a sleep specialist, sleep assessments conducted by a sleep technologist, tongue muscle function tests performed by a professional physical therapist, and blood collection by a professional nurse. Blood samples (20 cc each) will be collected at Week 0, Week 6 after the start of the project or post-surgery, and Week 18 after the start of the project

 or post-surgery, totaling three blood collections.

#### **Expected Results:**

For obstructive sleep apnea syndrome (OSA), this study proposes invasive upper airway surgery and non-invasive rehabilitation training. The invasive surgery targets common upper airway collapse sites based on the pathological development mechanisms of the condition, and post-surgery intervention involves muscle re-education for pharyngeal dilators through exercise therapy. This approach is expected to improve clinical symptoms of sleep apnea. Currently, sleep clinics provide home-based education by specialized nurses, but lack professional physical therapists for exercise training. This study aims to monitor and confirm the accuracy and effectiveness of exercise training through continuous and regular therapy. Additionally, the study will investigate the correlation between biomarkers and clinical symptoms, and the relationship between OSA severity and cardiovascular disease risk factors. The experimental design as a controlled study represents a significant milestone in the development of interdisciplinary teamwork and will serve as an important guideline for future clinical practice.

#### **Statistical analysis:**

Continuous variables are presented as mean and standard deviation (SD), whereas categorical variable is presented as numbers and percentages. Kolmogorov-Smirnov test was used to analyze the normal distribution of the variables. Due to the non-normal distribution, Kruskal–Wallis test and Fisher's exact test was used for continuous and categorical data to compare baseline characteristics among the study groups. Besides, the Wilcoxon signed-rank test was used to compare the pre- and post-differences in demographic characteristics, questionnaire, sleep parameters and the data of CT image. Linear regression model with generalized estimating equations (GEE) was used to estimate (1) the difference in differences and the corresponding 95% confidence intervals (CIs) of pre-treatment to post-treatment changes between the 3 groups and (2) multivariate adjusted effects of time in muscle strengths and biomarkers. The working correlation matrix was defined as unstructured. P < .05 was defined as statistically significant. All the statistical analyses were conducted by using SPSS 17.0.

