#### **Clinical Research:**

According to clinical examination of upper airway collapse sites, multiple interventions, including surgery and neuromuscular re-education training of the pharyngeal dilator muscles, will be implemented. The treatment modalities include sleep surgery and orofacial myofunctional therapy, to investigate their clinical efficacy for OSA. Using G power analysis, with a power level set at 80% and an alpha level at 0.05, the effective sample size is estimated to be about 28 subjects per group. The planned number of subjects for the experiment is 35 per group. The experiment is divided into two groups: the experimental group and the control group. The experimental group includes (1) a post-upper airway surgery group undergoing 12 weeks of orofacial myofunctional therapy (n=35) and (2) an upper airway surgery group (n=35). The control group consists of patients undergoing self-directed weight loss, using CPAP, and waiting for mandibular advancement devices (n=35). Given that the fabrication of mandibular advancement devices takes approximately 3-4 months, relevant measurements will be taken during the waiting period. For patients attempting self-directed weight loss, the principal investigator will inquire in the clinic if they are willing to receive professional weight loss consultation. (1) If the patient is willing, they will be referred to [name] weight loss clinic in the Family Medicine Department. (2) If the patient is unwilling, they will receive self-directed weight loss education materials, and a follow-up appointment will be scheduled 6 weeks later in the ENT clinic to check the weight loss status. If weight

loss is unsatisfactory, research assistant (physical therapist [name]) will arrange bi-weekly visits to measure weight and inquire about dietary status, providing food diaries, weight control diaries from the Family Medicine Department, and exercise diaries to ensure accurate recording and monitoring of weight loss. After 12 weeks, a follow-up appointment in the ENT clinic will confirm the weight loss status. All three groups will undergo pre- and post-intervention measurements and follow-up tests in a longitudinal study design to assess the effectiveness of functional training in physical therapy for post-surgical OSA patients.

**Objective 1:** Compare the different clinical outcomes between the two experimental groups to evaluate the clinical benefits of surgery combined with orofacial myofunctional therapy.

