**Table 1. Detailed Sampling Description** 

MFT: Y/Surgery: Z/Control: O	Week 0	Week 6	Week 18
Basic Data Collection			
Age, Gender, and Volumetric	Y/Z/O	Y/Z/O	Y/Z/O
Parameters			
Confounding Variables			
Medical History Record	Y/Z/O	Y/Z/O	Y/Z/O
Medication Record	Y/Z/O	Y/Z/O	Y/Z/O
Craniofacial Abnormality	Y/Z/O	Y/Z/O	Y/Z/O
Examination Record			
Sleep Clinical Symptoms Record	Y/Z/O	Y/Z/O	Y/Z/O
CT	Y/Z/O		Y/Z/O
Sleep-related Assessments			
Polysomnography	Y/Z/O		Y/Z/O
Drug-induced sleep endoscopy	Y/Z/O		Y/Z/O
Mental state assessment			
HADS	Y/Z/O	Y/Z/O	Y/Z/O
Muscle function tests			
Tongue	Y/Z/O	Y/Z/O	Y/Z/O
Pharyngeal Lateral Wall Muscles	Y/Z/O	Y/Z/O	Y/Z/O
Masticatory Muscles	Y/Z/O	Y/Z/O	Y/Z/O
Others	Y/Z/O	Y/Z/O	Y/Z/O
Biomarker test	Y/Z/O	Y/Z/O	Y/Z/O

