#### **Experimental Procedures and Methods:**

#### (1) Assessment Process:

Experimental Procedures and Testing Items: The experimental steps primarily

follow standard clinical procedures, detailed as follows:

- i. Screening through the sleep clinic to determine if further sleep-related assessments are needed (current clinical procedures).
- ii. Establishing the diagnosis of obstructive sleep apnea syndrome through sleep examinations (current clinical procedures, requiring overnight sleep studies at a sleep center).
- iii. Participants agree to self-weight management, use CPAP, await the fabrication of an anti-snoring dental appliance, or undergo sleep surgery.
- iv. Recruiting clinical participants based on inclusion and exclusion criteria, providing comprehensive study information, and informing participants of their right to withdraw from the study at any time. Participants will complete the consent form and will be orally introduced to the study grouping method during the clinic visit. Participants will choose their group based on personal preference and officially enter the clinical research study.
- v. Using computed tomography (CT) and drug-induced sleep endoscope examination to understand the pre-surgical pharyngeal anatomy.
- vi. Performing tongue muscle function tests, recording the results to understand pre-intervention functional indicators (approximately half an hour).
- vii. Conducting biomarker tests to understand pre-intervention biomarker indicators.
- viii. As detailed in Table 1, measurement parameters include sleep-related assessments, mental state assessments, drug-induced sleep endoscope examination, CT scans, respiratory-related muscle function tests, and biomarker tests. Pre- and post-surgical measurements, as well as follow-up measurements, will be conducted and repeated.
- Assessment Location: NCKU Hospital Physical Therapy Center

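### The between-group analysis of the primary outcomes is an unadjusted change-from-baseline contrast; a baseline-adjusted analysis should be reported beside it, with the assumption about group choice behind each stated.

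*Combined protocol and SAP*

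**What the plan says.** The Statistical analysis section (repeated in the Chinese text) gives the between-group result as a linear GEE model estimating "the difference in differences and the corresponding 95% confidence intervals (CIs) of pre-treatment to post-treatment changes between the 3 groups". It adds that "The working correlation matrix was defined as unstructured" and that "P < .05 was defined as statistically significant". No covariate is named for this contrast. The only adjustment mentioned is for "multivariate adjusted effects of time in muscle strengths and biomarkers", which are secondary outcomes, and its covariates are not listed.

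The primary outcomes are PSG with the ESS and PSQI questionnaires, sleep endoscopy (DISE) and CT. Table 1 schedules PSG at Week 0 and Week 18 only ("Polysomnography Y/Z/O Y/Z/O", with the Week 6 cell empty), and CT and DISE likewise. Figure 2 adds the questionnaires at Week 6.

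Groups are not randomised. Under Assessment Process, step ii is "Establishing the diagnosis of obstructive sleep apnea syndrome through sleep examinations", and step iv says "Participants will choose their group based on personal preference and officially enter the clinical research study". Objective 1 compares surgery plus myofunctional therapy (MFT) with surgery alone. For sample size, the Clinical Research section says "with a power level set at 80% and an alpha level at 0.05, the effective sample size is estimated to be about 28 subjects per" arm, and plans to enrol 35 in each.

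**The concern.** A change-score contrast fixes the slope of the Week 18 value on the Week 0 value at 1. Unless the true slope is 1, estimating it from the data gives a smaller residual variance. The Week 0 values are already collected, so the lost precision would cost nothing to recover. Adjusting for age or BMI would not do it, because the slope on the outcome's own baseline would still be 1.

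The second issue is bias. In self-chosen groups the change contrast and the baseline-adjusted contrast can differ systematically, and a plan that reports only one hides that. At stake is whether an Objective 1 finding for training depends on an unstated assumption about how patients chose their group.

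**Working it through.** **1. The plan's own figure.** The documents give no effect size, SD, test or sidedness, so 28 per group cannot be reproduced uniquely. Solving backwards at 80% power and alpha 0.05, 28 per group implies a standardised difference of 0.762 (two-sided t test), 0.749 (two-sided normal approximation), 0.673 or 0.665 (one-sided t or normal), or f = 0.345 (three-group ANOVA). The step to 35 matches 28/(1 − 0.20) = 35, but no dropout rate is stated. Below, 0.762 SDs of change at two-sided 0.05 is assumed to be what 28 per group was sized to detect.

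**2. What the planned model estimates.** In simulated three-group data with two visits, the group-by-time terms and their standard errors were identical under independence, exchangeable and unstructured working correlations. The estimates equalled the raw differences in mean change. The unstructured matrix therefore brings in no baseline adjustment.

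**3. Precision.** The inputs are rho (not in the plan, so assumed) and equal SDs at both visits (assumed).

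- Variance of change: 2(1 − rho)SD²
- Variance after baseline adjustment: (1 − rho²)SD²
- Ratio: (1 + rho)/2
- With a baseline gap of g SDs between two equal groups: multiply by (1 + g²/4)

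Adjusted power uses 0.762/√ratio. At rho 0.5 this is 0.762/√0.75 = 0.88.

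| rho | Ratio, balanced | Power at 28 per group (change: 80%) | n per group for 80% | Ratio, gap 0.5 SD |
|---|---|---|---|---|
| 0.3 | 0.65 | 93.5% | 19 | 0.69 |
| 0.5 | 0.75 | 89.9% | 21 | 0.80 |
| 0.7 | 0.85 | 86.0% | 24 | 0.90 |
| 0.8 | 0.90 | 84.0% | 26 | 0.96 |
| 0.9 | 0.95 | 82.0% | 27 | 1.01 |

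With a 0.5 SD gap, power is 88%, 84% and 82% at rho 0.5, 0.7 and 0.8. At rho 0.7 with a gap of 1 SD the ratio is 0.85 × 1.25 = 1.06, a loss. At 35 per arm, rho 0.5 and no gap, the standard errors are √(2 × 1.00/35) = 0.24 SD for change and √(2 × 0.75/35) = 0.21 SD adjusted.

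**4. Bias when training does nothing.** Simulation with 35 per arm. The choice mechanisms and gaps are assumed. A positive gap means that those choosing training start worse, and a negative bias looks like benefit.

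| Choice follows | rho | Gap (SD) | Change contrast: bias, false positives | Adjusted: bias, false positives |
|---|---|---|---|---|
| Measured Week 0 value | 0.5 | 0.47 | −0.24, 17% | 0.00, 5% |
| Measured Week 0 value | 0.7 | 0.47 | −0.15, 13% | 0.00, 5% |
| Stable severity | 0.5 | about 0.45 | 0.00, 5% | +0.24, 20% |
| Stable severity | 0.7 | about 0.45 | 0.00, 4% | +0.14, 13% |
| Neither | 0.5 or 0.7 | 0 | 0.00, about 5% | 0.00, about 5% |

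Arithmetic check: the bias is about (1 − rho) × gap, for example 0.5 × 0.47 = 0.235.

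If surgery also narrows the spread (Week 18 SD assumed to be 0.6 of Week 0) and choice follows stable severity, both are biased, in opposite directions. At rho 0.5 the change contrast gives −0.13 SD (10% false positives) and the adjusted model +0.11 SD (14%). At rho 0.7 the figures are −0.16 SD (16%) and +0.07 SD (11%).

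**The case against.** The strongest reply is that difference in differences is a recognised choice for preference-based groups because it removes stable differences between them. If choice follows stable severity, and the groups would otherwise change equally, the planned contrast is unbiased and the adjusted model is not. The errors are nearly the mirror image of the opposite case. This stands, and it rules out replacing the planned contrast with the adjusted one as the sole Objective 1 result.

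A reader might also infer that patients choose on the diagnostic PSG, so that regression to the mean produces an apparent training effect. The documents do not support that:

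- They give personal preference as the basis for choice, and nothing links choosing training to the PSG value.
- Both Objective 1 arms have surgery, so a PSG-driven gap is more plausible between surgery and control.
- Steps v to vii list no new PSG after consent, but they also omit the anxiety and depression scale that Table 1 schedules at Week 0. The list is partial and cannot exclude a fresh baseline PSG.
- CT and DISE come at step v, after the choice, so patients cannot have chosen on those results.
- The ESS entry threshold of 10 is the same for all groups, so the regression it causes largely cancels if the groups are otherwise alike.

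Finally, the balanced-baseline power gains and the bias figures assume different baseline gaps and should not be quoted together.

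The reply does not justify reporting the change contrast alone. Its validity rests on equal change in the absence of training, which fails if milder and more severe patients respond to surgery by different absolute amounts.

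**Conclusion.** The point holds as a request for a second, baseline-adjusted analysis of the primary outcomes. The precision loss is real when baselines are similar: a variance ratio of 0.65 to 0.90 for rho 0.3 to 0.8, or about 4 to 14 points of power if 28 per group was sized for 80% on change. Its size rests on a correlation that the plan does not give, and it disappears at about rho 0.9 with a 0.5 SD gap.

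Bias from choosing on the measured PSG is possible but not documented. Which of the two models should lead is a trade-off that the documents cannot settle. In every mechanism simulated, at least one estimate was unbiased or the two fell on opposite sides of the truth, so reporting both shows whether the Objective 1 conclusion depends on how patients chose. This was seen in the cases tried and is not a guarantee. Agreement between the two does not remove confounding by preference.

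**What to change.** In the Statistical analysis section, in both languages:

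1. Keep the GEE difference in differences.
2. For each continuous primary outcome, add a linear model of the Week 18 value on group plus the Week 0 value of the same outcome. For ESS and PSQI, model the post-baseline visits with baseline and baseline-by-visit terms.
3. Report both estimates with 95% confidence intervals for surgery plus MFT versus surgery alone.
4. State what each assumes. The difference in differences is unbiased if choice follows stable severity and the groups would otherwise change equally. The adjusted model is unbiased if choice follows the measured Week 0 value.
5. Claim a training effect as robust only if both agree, and treat disagreement as a sign of selection.
6. State that neither model removes confounding from preference-based allocation.

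The cost is a few sentences and one more analysis of data already collected, with no new visits or measurements. The downside is that discordant results may have to be explained.

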#### • Biomarker Research:

This study will measure biomarkers including 8-hydroxy-2-deoxyguanosine (8-OHdG), malondialdehyde (MDA), superoxide dismutase (SOD), catalase (CAT), nuclear factor kappa B (NF-κB), tumor necrosis factor-α (TNF-α), interleukin 6 (IL-6), and matrix metalloproteinase 9 (MMP-9). Previous literature indicates that the repetitive ischemia and reperfusion injuries associated with OSA lead to excessive production of reactive oxygen species (ROS), oxidative stress substances (such as 8-OHdG and MDA), and inflammatory precursors (such as TNF-α and IL-6), which damage antioxidant capabilities. Oxidative stress substances can increase ROS levels, which activate NF-κB, a transcription factor that stimulates the production of inflammatory precursors and regulates the transcription of MMPs. The activation of TNF-α, IL-6, and MMP-9 can impair endothelial cell function, potentially leading to cardiovascular disease. Research has shown significant increases in serum levels of 8-OHdG, MDA, NF-κB, TNF-α, IL-6, and MMP-9 in OSA patients, while antioxidant stress substances (SOD and CAT) show significant decreases. MDA, NF-κB, and MMP-9 levels are highly positively correlated with the duration of nocturnal oxygen saturation below 85%, and negatively correlated with the average blood oxygen saturation. Additionally, MMP-9 levels are positively correlated with plasma IL-6 and TNF-α levels. This study aims to understand the correlation between the severity of OSA and cardiovascular disease risk factors and to explore whether surgical and

exercise interventions improve these risk factors.

Objective 4: Investigate the correlation between the severity of OSA and cardiovascular disease risk factors.

Objective 5: Examine whether exercise intervention improves cardiovascular disease risk factors and mental state.

[figure not shown]

Figure 1. Experimental Flow Diagram

Experimental Equipment: Figure 2, Table 1

- A) Primary Outcome Measurements:
- Sleep-related assessments:
- i. PSG (Polysomnography) including sleep quality questionnaires: ESS (Epworth Sleepiness Scale), PSQI (Pittsburgh Sleep Quality Index)
- ii. Drug-induced sleep endoscope examination (DISE)
- Computed Tomography (CT)
- B) Secondary Outcome Measurements:

- Respiratory-related muscle function tests:
- i. Tongue muscle (Genioglossus): Iowa Oral Performance Instrument (Medical LLC, Carnation, WA)
- ii. Masticatory muscle function: Dynamometer

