#### 統計分析:

連續變數以均值和標準差(SD)表示,而分類變數以數量和百分比表示。使用 Kolmogorov-Smirnov 檢驗來分析變數的正態分布。由於分布不符合正態分布,對於連續數據和分類數據,分別使用 Kruskal - Wallis 檢驗和 Fisher 精確檢驗來比較研究組之間的基線特徵。此外,使用 Wilcoxon 符號秩檢驗比較人口特徵、問卷、睡眠參數和 CT 圖像數據的前後差異。使用帶有廣義估計方程(GEE)的線性回歸模型來估計(1)治療前後三組間差異的差異及其對應的 95%置信區間(CIs),以及(2)時間對肌肉力量和生物標誌物的多變量調整效果。工作相關矩陣定義為非結構化。P<0.05 被定義為統計學上顯著。所有統計分析均使用 SPSS 17.0 進行。

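### Participants choose their arm, yet the between-arm contrast that answers the training questions has no stated covariate adjustment; adjustment is stated only for an effect of time, which has no comparator

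*Combined protocol and SAP*

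**What the plan says.** Item iv of the assessment process (Experimental Procedures and Methods) lets participants enter the group they prefer; nothing is randomised. The arms are surgery followed by 12 weeks of orofacial myofunctional therapy (MFT), surgery alone, and a control arm of weight loss, CPAP or waiting for a mandibular device.

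Two objectives concern training:
- Objective 1: "Compare the different clinical outcomes between the two experimental groups to evaluate the clinical benefits of surgery combined with orofacial myofunctional therapy".
- Objective 5: "Examine whether exercise intervention improves cardiovascular disease risk factors and mental state".

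The Statistical analysis section gives one GEE linear model with two outputs:
- Part (1): "the difference in differences and the corresponding 95% confidence intervals (CIs) of pre-treatment to post-treatment changes between the 3 groups". It is not limited to particular outcomes, and no covariates are mentioned.
- Part (2): "multivariate adjusted effects of time in muscle strengths and biomarkers". The Chinese text says the same: "時間對肌肉力量和生物標誌物的多變量調整效果". The covariates are not named in either language.

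It also states that "the Wilcoxon signed-rank test was used to compare the pre- and post-differences in demographic characteristics, questionnaire, sleep parameters" and CT data. Baseline characteristics are compared among groups by Kruskal–Wallis and Fisher tests. Table 1 lists medical history, medication, craniofacial findings and sleep symptoms as confounding variables, but no section puts them into a model.

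**The concern.** People who opt for surgery plus a 12-week exercise programme may differ from people who opt for surgery alone, for example in OSA severity or body mass index. If such factors also affect how much a patient changes, the difference in differences attributes part of their effect to training. As written, the contrast that can isolate training carries no stated protection against this, while the output that is called adjusted does not compare arms. A reader of the results could take an adjusted time effect on a biomarker as evidence for exercise, when in the MFT arm it also contains surgery and recovery.

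**Working it through.** **1. The plan's own figure.** The protocol gives 28 per group (80% power, alpha 0.05) and plans 35. No effect size is stated, so 28 can be neither confirmed nor refuted. Solved backwards, two-sided: d = (1.960 + 0.842) × √(2/28) = 0.749. Also 28/0.80 = 35, but no dropout rate is stated, and 3 × 35 = 105 agrees with the stated total. The point does not depend on these figures; 28 and 35 serve below only as n per arm.

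**2. The planned analyses side by side.**

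| Analysis | Compares arms on change? | Adjustment stated? |
|---|---|---|
| GEE part (1), difference in differences | Yes | No |
| GEE part (2), effect of time | No | Yes, covariates unnamed |
| Wilcoxon pre-post | No | No |
| Kruskal–Wallis, Fisher | No, Week 0 only | No |

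**3. What self-selection leaves in the difference in differences.** Let the Week 0 to Week 18 change be D = common change + θ (MFT arm only) + b·X + error, where X is a Week 0 covariate. Anything that shifts both visits equally cancels in D. The contrast between the surgical arms estimates θ + b × (difference in mean X).

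Assumed inputs, none from the documents: θ = 0, imbalance 0.5 SD, b = 0.3 to 0.5 SD per SD, within-person correlation r = 0.5 or 0.7.
- Bias: 0.3 × 0.5 = 0.15 SD; 0.5 × 0.5 = 0.25 SD.
- SD of change: s = √(2(1−r)) = 1.000 or 0.775. If the covariate's variance is added on top, s = √(2(1−r) + b²).
- Noncentrality = bias / (s√(2/n)), two-sided t test at 5%.

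| Setting | n=28 | n=35 |
|---|---|---|
| Lowest: b=0.3, r=0.5, variance added (s=1.044) | noncentrality 0.538, 8.3% | 0.601, 9.1% |
| Highest: b=0.5, r=0.7, total SD fixed (s=0.775) | 1.208, 22.0% | 1.350, 26.5% |

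Simulation with total SD fixed put the upper ends at about 23% and 26%. With the variance added on top, they are 17% and 20%. Adjusting for X brings bias to 0.00 and rejection to about 5%, but by construction, because X is the only confounder in the illustration.

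**4. Why the form of adjustment matters.** A Week 0 covariate entered as a main effect adds the same amount at every visit and drops out of D. Only a covariate-by-visit term enters D. One simulated complete dataset (three arms of 28, three visits, true contrast 0) gave an MFT-minus-surgery interaction of 0.2239 without the covariate, 0.2239 with its main effect, and −0.1808 with covariate-by-visit terms. A single dataset shows only that the estimate moves, not that it is nearer the truth. With 20% of Week 18 values removed, the main effect did shift the contrast slightly (0.1555 to 0.1771), so exact invariance needs complete data and time-fixed covariates.

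**5. What a time effect detects.** With a surgical change of 0.3 to 0.5 SD and no exercise effect, a one-sample test of change in the MFT arm (noncentrality = change / (s/√n)) is significant in 33 to 91% of trials at n=28 and 41 to 96% at n=35. This is power to detect change over time. It is not an error rate of any exercise test in the plan.

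**6. Precision cost.** This is the ratio of mean CI widths when the covariates predict nothing, at imbalances of 0, 0.3 and 0.5 SD each, with n=28. Three covariates: 1.030, 1.066, 1.126. Four covariates: 1.040, 1.087, 1.167.

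**The case against.** The strongest reply is that the right contrast is already planned. Part (1) covers all three groups, gives confidence intervals and is not restricted by outcome, and no section assigns part (2) to the exercise question. That stands: a reader might infer that the plan tests exercise through a time effect, but the documents do not say so.

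Other replies also stand in part:
- A reader might infer that part (1) is unadjusted. The text supports only that no adjustment is stated, because one model yields both outputs and might share covariates.
- A reader might infer that every difference between self-selected arms biases the contrast. Stable additive differences cancel; only factors that affect change remain.
- A reader might say that time effects can never separate surgery from training. The Chinese flow chart labels Week 6 as a post-surgery measurement, and 6 + 12 = 18, so training may fall between Weeks 6 and 18. The start week is not stated, though, and recovery overlaps that window.
- The plan does not say that covariates enter as main effects only. Table 1 repeats the confounder records at Weeks 6 and 18, so time-varying adjustment is not excluded. Those later values may be affected by treatment, which is a reason against using them.

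None of this supplies a covariate set for the between-arm contrast.

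**Conclusion.** The point holds in this form and should be fixed: arms are self-chosen, confounders are recorded, and neither language version says that the contrast answering Objective 1 and the exercise question in Objective 5 is adjusted for them. The output that is called adjusted has no comparator.

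The sizes in steps 3 and 5 show direction and range under assumed inputs; they do not estimate the bias in this trial. Adjustment removes only the part due to the measured covariates. The stronger conclusions that the plan lacks a usable exercise contrast, or that self-selection defeats difference in differences altogether, are not supported. Confidence is high on what the text states and omits, and low on the size of any actual bias.

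**What to change.** 1. Name surgery plus MFT minus surgery alone in the Week 0 to Week 18 change, with 95% CI, as the contrast for Objective 1 and the exercise question in Objective 5. Report the Week 6 to Week 18 contrast as well for outcomes measured at Week 6. Keep the contrasts with control for the broader aim, which covers "cardiovascular disease risk factors and to explore whether surgical and" exercise interventions improve those factors.
2. Adjust this contrast for a small fixed set of Week 0 covariates already collected: age, gender, body mass index and one named PSG severity measure. For PSG outcomes, the Week 0 value of the outcome can serve as the severity term. Enter the covariates with covariate-by-visit terms, and do not use Week 6 or Week 18 values as covariates.
3. Apply the same adjusted group-by-visit contrast to muscle strength and biomarkers. State that time effects and Wilcoxon pre-post tests are descriptive with respect to exercise.
4. Report the result as an adjusted comparison of self-selected arms. The phrase "Due to the non-normal distribution" suggests that data may already have been examined; if so, label the adjusted analysis post hoc.

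The cost is SAP wording, plus a re-run if the analysis has been done. No new measurement is needed. With 3 to 4 covariates that predict nothing, the CI is roughly 3 to 17% wider at n=28 (2 to 16% at n=35). Unmeasured self-selection, such as motivation, remains.
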